At 3 and 9 month time points between annual visits, telephone surveying of medication compliance will be obtained. Any adverse events (AE) will be reviewed. A 24-hour phone number will be provided to participants to call in the event of any adverse outcome between these contact points. Additional phone calls may be made if subjects are found to be non-compliant.

All study participants will receive a telephone call to remind them to fast for 12 hours prior to their study visit.

Participants enrolled in the muscle biopsy substudy will receive a telephone call within 3 days prior to their biopsy visits to remind them to fast for 12 hours prior to the visit, to remind them to abstain from vigorous physical activity, and to ensure they are not on anticoagulant or antiplatelet medications within 7 days from the biopsy visit.

Half-Yearly Visits (6 months; Year 1 +6 months; Year 2 +6 months)

Half-yearly visits will occur at 6 Months, Year 1 + 6 Months, and Year 2 + 6 Months. All subjects will go to VAPORHCS for these visits. For those in the substudy, only for the 6 Month visit, they will also go to OHSU after labwork is drawn at VAPORHCS.

This visit could take up to 2 hours for participants (3 hours for participants in the muscle biopsy substudy at the 6 Month visit). At each half-yearly visit, all participants will have fasting labwork drawn, and have questionnaires reviewed and completed. Subjects >80 years old will get labs checked for creatinine and eGFR. Participants in the muscle biopsy substudy will undergo muscle biopsy if their morning STAT labs demonstrate platelet, INR, and aPTT levels in the normal range. Participants will be given breakfast after fasting lab work/muscle biopsy has been obtained.

Annual Visits (Years 1, 2, and 3)

These annual visits could take up to 3 hours. The participants will first get a fasting blood draw. They will then be given breakfast before proceeding with the following study measures: review and completion of questionnaires, medication inventory, physical performance tests, and whole body DXA.

Study Drug

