We have chosen to study metformin in this clinical trial due to the observation that metformin use was associated with an attenuated loss of muscle mass and function in our preliminary studies. While both metformin and thiazolidinediones can upregulate AMPK and PGC1a in muscle to increase muscle fatty acid oxidation, angiogenesis, mitochondrial biogenesis and oxidative muscle fibers for healthier-appearing muscle,^{32, 34, 68} metformin has additional benefits on mortality, microvascular and macrovascular outcomes in patients with type 2 diabetes;⁶⁹ whereas, thiazolidinediones have associated risks of adverse cardiovascular outcomes.^{70, 71}

The VA Research Pharmacy will be used to randomize, dispense, and track blinded placebo and metformin tablets in 3-month supplies. A covariate-adaptive randomization scheme will be used to ensure equal age, gender and race distributions. The investigators and study participants will be blinded to the randomization of the study drug assignments. A 90-day supply of study drug will be mailed every 3 months to participants with a pre-paid envelope for returning unused study drugs for pill counts. An additional 4-day buffer may be included to avoid lapses in study drug administration due to unforeseen complications in medication delivery and/or receipt. To minimize self-limiting gastrointestinal side effects, participants randomized to metformin will begin with an oral dose of 850 mg tablets once daily (taken with meals) for 1 month with titration up to 850 mg twice daily for the remainder of the study. We anticipate an effect on muscle using this dosage, since a significant reduction in peripheral insulin resistance occurs even with a metformin daily dosage of 750 mg.⁶¹ Furthermore, this dose was safe and effective in lowering the risk of diabetes for subjects with prediabetes in the Diabetes Prevention Program.⁷⁵ Plans for monitoring and preventing risks associated with metformin are further discussed under Human Subjects.

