Instances where the study drug is discontinued include the following: development of a contraindication to metformin as described under the section for exclusion criteria; development of lactic acidosis; diagnosis of diabetes; hospitalization; 48 hours prior to procedures or scans that require contrast medium; or development of B12 deficiency. For those who are hospitalized or receive contrast medium, efforts will be made to recheck kidney function within 48 hours after discharge/procedure and the study drug will be restarted if there is no evidence of renal dysfunction. For tests or procedures that require fasting, study drug will be stopped 24 hours prior to test or procedure, and study drug can be resumed after the participant is allowed to eat again. Compliance to study drug will be tracked and accounted for in analyses.

Study Procedures

All study procedures are research-related.

Exam: Exams for annual visits will occur at OHSU after fasting labwork has been drawn at VAPORHCS. At Screening, baseline and yearly exams, height will be measured in meters using a wall-mounted Harpenden stadiometer, body weight will be measured in kilograms using a balance beam scale, waist and hip circumference measured with a tape measure, and measurements of pulse and blood pressure will be taken.

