dehydrogenase staining and quantification using image analysis of staining intensity will be assessed as described.⁷⁵ Triglyceride content will be determined using Oil Red O staining using established methods.⁷⁸ Capillary density (number of capillaries/muscle area) will be determined by visualization using a tetramethylrhodamine isothiocyante (TRITC) excitation filter after thawed and air dried sections are fixed in 0.25% formaldehyde, incubated with lectin and rinsed.³⁶ The percentage of Type I, IIa and IIx fibers will be determined from manual counting 100-300 fibers in stained sections. The sections will first be incubated overnight at room temperature with antibodies against antihuman myosin heavy chain-7 (type I fibers) and myosin heavy chain-2 (type IIa fibers) and then incubated with secondary antibodies conjugated with fluorescein (type IIa fibers) and rhodamine (type I fibers) . Type IIx fibers will remain unstained. Images will be acquired with an optical microscope.^{36, 74} Diacylglycerol and ceramide content will be measured using high-performance liquid chromatography-tandem mass spectrometry from a homogenized (using ice-cold buffer of 250 mM sucrose, 25 mMKCl, 50 mMTris, and 0.5 mM EDTA, pH7.4) liquid nitrogen-frozen sample as previously described.³⁶

Meals

After fasting labwork/biopsies have been taken, participants will be provided breakfast by the OCTRI Bionutrition Unit.

Schedule of Study Procedures

	Screening	Baseline	Baseline	3 and 9 Months,	6 Month	Years 1,	Year 1 + 6
	Visit	Visit ^a	Muscle	Year 1 +3 and +9	Visit^d	2, and 3/	Months,
			Biopsy	Months, Year 2 +3		End of	and Year 2
			Visit^b	and +9 Months		Study	+ 6 Months
				Phone Calls ^c		Visit ^d	Visits ^d
Consent	Х						
Inclusion/Exclusion	Х						
Height	Х					Х	
Weight, blood pressure	Х	Х				Х	
Demographics	Х						
Medical History	Х						
Questionnaires		Х			Х	Х	Х
Labs		Х			Х	Х	Х
Fasting Glucose	Х	Х				Х	
Fasting Insulin		Х				Х	
ALT	Х					Х	
AST	Х					Х	
Creatinine	Х				Xf	Х	Xf
eGFR ^e	Х				X ^f	Х	X ^f
B12	Х					Х	
Platelets	Х				X ^g		
INR, aPTT	Х				X ^g		
Biorepository		Х			Х	Х	Х
Physical Performance	Х	Х				Х	
DXA		Х				Х	
Muscle Biopsy (only for			Х		Х		
substudy) ^h							
Concurrent	Х	Х			Х	Х	Х
medications							
Medication compliance				Х	Х	Х	Х
AE monitoring				Х	Х	Х	Х
Meals		Х	Х		Х	Х	Х

^aBaseline visit will occur 14 ± 7 days from Screening visit.

^bFor substudy, Baseline Muscle Biopsy visit will occur within 14 days from Baseline visit.

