By enrolling participants without liver or kidney dysfunction or congestive heart failure, the risk of lactic acidosis or hepatitis on metformin will be decreased. Furthermore, we intend to prevent such risks by screening liver and kidney function every year in all participants and quarterly in adults aged 80 or greater and stopping metformin in participants who develop evidence of liver/kidney dysfunction for their safety. Per 2016 FDA guidelines, metformin use will be discontinued if the eGFR drops below 45 mL/min/1.73 m2. For those who are hospitalized or receive contrast medium, the drug will be held and efforts will be made to recheck kidney function within 48 hours after discharge/procedure. The study drug will be restarted only if there is no evidence of renal dysfunction. For tests or procedures that require fasting, study drug will be stopped 24 hours prior to test or procedure, and study drug can be resumed after the participant is allowed to eat again. Participants with B12 deficiency will not be enrolled in the study, and B12 levels will be monitored throughout the study. If B12 deficiency is found, the participant will discontinue study drug. Initial weight loss due to gastrointestinal symptoms is usually self-limiting and continued metformin use is associated with weight stability.⁴ We have chosen a slow titration up of metformin dosage from 850 mg qd to 850 mg bid to allow for minimization of self-limiting gastrointestinal distress and plan to carefully monitor weight and dietary intake at each study visit. If participants report symptoms of lactic acidosis during screening for adverse events, laboratory confirmation will be sought and study drug cessation if found.

Protection Against Risks of Diagnosis - From labs at Screening and study visits, diabetes may be diagnosed (defined by fasting plasma glucose≥126 mg/dL). Participants will be notified and referred to their primary care physician.

Protection Against Risks of Study Procedures

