Potential benefits to participants include the detection and potentially earlier treatment of diabetes mellitus. Participants in both metformin and placebo groups will benefit from routine lifestyle modification counseling at yearly visits for prevention of diabetes.

Others may benefit from a greater understanding of the effect of metformin on muscle mass and function in insulin-resistant older adults.

VA Data Monitoring Committee (DMC)

A data monitoring committee will be provided by VA CSR&D. With DMC's experience in the conduct and monitoring of clinical trials, it will assist with ensuring the overall safety of study participants, assessing safety and efficacy of the study intervention, monitoring the overall conduct of the clinical trial including recommendations on recruitment and retention of participants and improvement of study drug adherence, and providing recommendations on stopping or continuation of the trial. SAEs and UPRs will be reported to the DMC. For further details, see the "Instructions for the Review of New (uninitiated) Protocols by DMC Members."

Inclusion of Women and Children

Because sarcopenia is a condition of older age, children will not be enrolled in this study. Women will be included in a proportion reflective of their gender distribution at the VAPORHCS.

Criteria for Discontinuation

Subjects will be withdrawn from further study drug administration in the event of any of the following:

• Diagnosis of diabetes

- If hospitalized for any reason and after 48 hours of discharge, there is evidence of renal dysfunction
- If they require contrast medium and after 48 hours of procedure, there is evidence of renal dysfunction
- Developed lactic acidosis
- Developed renal insufficiency at the level indicated by the FDA ($eGFR < 45 \text{ mL/min}/1.73 \text{ m}^2$).
- Development of B12 deficiency
- Excessive alcohol intake
- Subject withdraws consent
- Significant deviation from the protocol or eligibility criteria in the opinion of the investigator
- Any other reason that in the opinion of the investigator, would justify removing the subject from the study

There are no pre-defined stopping rules for termination of the study.

VA Research:

The following are the components of the study which will be conducted at the VAPORHCS:

- Advertising
- Recruitment
- Study visit activities at Screening, Baseline, half-yearly visits, and annual visits
 - Consent
 - Height, weight
 - o Blood pressure
 - Demographics
 - Medical history

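### The metformin risk section promises a weight check at each study visit, but the exam text and the schedule leave out months 6, 18 and 30, so the first scheduled on-treatment weight is at month 12

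*Combined protocol and SAP*

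**What the plan says.** Four parts of the combined protocol and SAP bear on when participants are weighed.

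- **Protection Against Risks of Metformin Use.** After noting that early loss from gastrointestinal upset usually resolves without treatment, and that the dose is raised slowly, the section says the team will "plan to carefully monitor weight and dietary intake at each study visit".
- **Study Procedures, Exam.** "At Screening, baseline and yearly exams, height will be measured in meters using a wall-mounted Harpenden stadiometer, body weight will be measured in kilograms". Half-yearly visits are not named.
- **Schedule of Study Procedures.** The row "Weight, blood pressure" is marked at Screening, Baseline and the annual visits. It is blank for the 6-month visit and for the two later half-yearly visits.
- **Half-Yearly Visits.** "At each half-yearly visit, all participants will have fasting labwork drawn, and have questionnaires reviewed and completed". No weighing is mentioned. The Compensation section likewise describes these visits as labs and questionnaires only, and names weight among the procedures of the baseline and annual visits.

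On dose, the Study Drug section starts metformin participants on "850 mg tablets once daily (taken with meals) for 1 month with titration up to 850 mg twice daily".

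**The concern.** The risk section presents weight monitoring as one of the ways participants are protected. The sections that tell staff what to do at each visit do not provide it at half of the follow-up visits. The gap falls where the promise matters most. The stated worry is loss soon after starting the drug, yet no weight is scheduled between Baseline and month 12.

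Participants are at least 65 years old and must be weight-stable at entry, and the exclusion criteria list weight loss among the lifestyle factors that affect muscle. That is an entry criterion and sets no on-treatment monitoring rule. It does show why the investigators would want to know about a loss.

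What is at stake is a small safety measure and the agreement of the document with itself.

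**Working it through.** The check is a count of visits. The plan gives no figure to reproduce.

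**Inputs**

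- Follow-up clinic visits: half-yearly at months 6, 18 and 30, and annual at months 12, 24 and 36 (Half-Yearly Visits; Annual Visits). Phone contacts and the baseline biopsy visit are not counted.
- Visits with a scheduled weight after Baseline: months 12, 24 and 36 (Exam text and schedule row).
- Move to full dose: after 1 month (Study Drug).
- Participants randomised: 120 (Study Population).

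**Step 1: is the blank real?** The weight row in the schedule has all seven cells, with marks in cells 1, 2 and 6. The questionnaire row is marked in cells 2, 5, 6 and 7, and the creatinine row in cells 1, 5, 6 and 7. Marks in the half-yearly columns (5 and 7) therefore survive in the table where they were entered. The Exam paragraph gives the same timing for weight in prose, so the reading does not depend on the table alone.

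**Step 2: count.**

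| Month | 6 | 12 | 18 | 24 | 30 | 36 |
|---|---|---|---|---|---|---|
| Clinic visit | yes | yes | yes | yes | yes | yes |
| Weight scheduled | no | yes | no | yes | no | yes |

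Visits without a weight: 6 − 3 = 3.

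**Step 3: timing**, taking Baseline as month 0 and drug start as close to it.

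- First on-treatment weight: month 12, which is 12 − 1 = 11 months after the step to full dose.
- Longest gap between weights: 12 − 0 = 12 months.

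**Step 4: with weight added at the half-yearly visits.**

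- Visits with a weight: 6 of 6.
- First on-treatment weight: month 6, which is 6 − 1 = 5 months after the step to full dose.
- Longest gap: 6 months.
- Added weighings: at most 120 × 3 = 360 before dropout, or 120 × 1 = 120 if only month 6 is added.

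**Step 5: the dietary half of the promise.** The Questionnaires paragraph sends out diet questions before every visit from Baseline to the end of study, and the schedule marks questionnaires at the half-yearly visits. That half is met, so only weight is at issue.

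**The case against.** **The site lists may already cover it.** The VA Research section names weight under the heading "Study visit activities at Screening, Baseline, half-yearly visits, and annual visits", and the OHSU Research list names it under a heading that includes the 6-month visit. These lists pool several visits. The VA list also contains consent and demographics, which the schedule places at Screening only. They neither assign a weight to the half-yearly visits nor rule one out.

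**Silence proves little.** This stands in part. The Half-Yearly Visits text is not exhaustive, the Annual Visits text does not mention weight either, and the Compensation summary omits adverse event review, which the schedule does mark. The schedule has gaps of its own: height is blank at Baseline, and waist and hip have no row. The point therefore rests on the Exam text and the schedule agreeing with each other and differing from the risk section.

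**The benefit is small.** This stands. A brief early loss could be over by month 6, and weights at months 18 and 30 do nothing for initial loss. The Criteria for Discontinuation contain no weight threshold, so a recorded loss would lead to action only through the investigator's judgement. Other cover exists: the slow titration, an adherence call at month 1, adverse event review at months 3, 6 and 9, and a 24-hour phone number.

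**Stronger readings.** A reader might infer that participants will in fact go unweighed for a year. The documents show only that no weight is scheduled. A reader might also infer that the muscle results are compromised, or that weight must be reported by arm or shown beside the 6-month biopsy findings. The documents do not support this: weight is scheduled at every visit that has a DXA scan, and nothing ties the promised weight monitoring to histology or to a comparison of arms.

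**Conclusion.** The inconsistency is real and minor. The risk section promises weight at each study visit. The two places that set the timing of weight omit 3 of 6 follow-up clinic visits, and the first scheduled on-treatment weight is at month 12. This is more than a wording slip, because the omitted measurement is a protection that the protocol itself states and could provide at almost no cost. It is not a serious safety failure, because symptoms are followed by other means. No endpoint, power figure or randomised comparison changes.

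The conclusion assumes that study visit includes the half-yearly visits, which the protocol calls visits throughout, and that the Exam text and the schedule govern over the pooled site lists.

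**What to change.** 1. In the Schedule of Study Procedures, mark weight in the 6-month visit column. This is the priority, because it is the earliest clinic visit after treatment starts.
2. Mark weight also in the column for Year 1 + 6 months and Year 2 + 6 months, so that the schedule matches the promise in full.
3. Amend Half-Yearly Visits, the Exam paragraph and the Compensation summary to agree.
4. Record which scale is used. For the half-yearly visits, "All subjects will go to VAPORHCS for these visits", whereas "Exams for annual visits will occur at OHSU after fasting labwork has been drawn at VAPORHCS". A change in weight between visits could otherwise reflect the scale.

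The cost is a schedule amendment and at most 360 weighings, with no new visits. If the team prefers not to weigh at these visits, it could narrow the sentence in the risk section to the annual visits. That makes the document consistent but gives up the stated first-year safeguard, so adding the weights is the better choice.
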